Appendix I - Pathways for Introduction of VMMC Devices

This schematic shows three potential alternative pathways for introducing a new prequalified device into voluntary medical male circumcision programs, based on extent of previous experience with device introduction. All are consistent with the WHO Framework for Clinical Evaluation of Devices for Male Circumcision, 2012, designed to ensure appropriate safety monitoring in introduction.*

* These pathways do not apply to bridging studies
† Current classes are collar clamp and elastic collar compression.

Regardless of pathway, preparation for introduction and implementation of a new technology should follow a participatory planning process that includes all key stakeholders. *Beginning with the end in mind: planning pilot projects and other programmatic research for successful scaling up* (WHO 2011) provides a framework on how to design pilot projects with scaling up in mind to increase the likelihood that they can be implemented on a large scale if proven successful.

Appendix VII – Case Report Form (CRF) – Screening

CASE REPORT FORM - SCREENING

Evaluation of the safety and acceptability of the ShangRing device for male circumcision in
Tanzania

Site Code:

Client ID # (CID):

*A copy of the full SOP Manual is available upon request.

INSTRUCTIONS FOR THE PROPER COMPLETION OF THE CRF

Please follow the instructions below:

1. Use a ball-pen, DO NOT use a pencil, a marker or a fountain pen.
2. Make sure to place the separator provided under the last copy of each page so that data recorded on one page does not copy to the next.
3. Subject initials will be comprised of the first letter of the first name followed by the first letter of the surname.
4. Fill in the form in a clear, concise and readable way. Use common medical terminology.
5. Correct wrong data by crossing out the information with a single line and writing the correct data next to it. The evaluation coordinator, or the site coordinator in the evaluation coordinator's absence, will initial and date the correction.
 - a. Example: 07/03/1969 corrected to 09/03/1969 (with initials and date of the correction)
6. Complete all the available boxes, DO NOT leave empty fields.
 - a. For evaluations not performed record ND (not done).
 - b. For data not relevant to the subject or stage of evaluation record NA (not applicable).
 - c. If you do not know the data, please use the initials UNK (unknown).
 - d. Use leading zeroes if necessary (e.g.: 15 mg = 0 1 5 mg).
 - e. Make sure to complete every header on each page.
7. Please make sure to **circle the correct option** whenever it is requested.
8. Please DO NOT add wording to CRF pages unless required. For any additional comments please use the Comments Sheet at the end of the CRF modules.
9. Dates (e.g., date of birth, date of visit) will be recorded in the DD/MM/YYYY format.
 - a. Example: 19 June 2017 will be recorded as 19/06/2017
10. CID is the Client Identification Number. It comprises the initials of the site followed by the four digit enrollment date and the three digit subject consecutive number. Example: Subject number 1 in Good Hope Health Center enrolled on July 21 will be GH2107001.
11. Time will be recorded in 24:00 format.
 - a. Example: 6:15 pm will be recorded as 18:15

Client's CID:

ELIGIBILITY CONFIRMATION

Inclusion Criteria	(check appropriate box)	
Male 13 years or older	Yes 	No 
Wants to be circumcised	Yes 	No 
Is uncircumcised	Yes 	No 
HIV sero-negative	Yes 	No 
Able to communicate in English or Swahili	Yes 	No 
Lives within 30 km of the facility	Yes 	No 
Agrees to be circumcised using the ShangRing device	Yes 	No 
Capable and willing to provide written informed consent (18 years and older), or written informed consent from parent (13-17 years)	Yes 	No 
If 13-17 years old, parent/guardian agrees to be present during circumcision (skip if client is older than 17)	Yes 	No 
Penis fits into one of the 18 ShangRing ring sizes	Yes 	No 
Able to understand the evaluation procedures and requirements	Yes 	No 
Agrees to abstain from sexual intercourse and masturbation, for six (6) weeks post removal (i.e., seven (7) weeks total)	Yes 	No 
Willing to provide valid contact information (i.e., telephone number, address of residence, place of employment and other locator information)	Yes 	No 
Has an activated cell/mobile phone or access to a cell/mobile phone	Yes 	No 
Agrees to complete brief evaluation surveys to assess satisfaction: post-placement and post-removal	Yes 	No 

Any "NO" answer disqualifies the subject from participating in the evaluation

Exclusion Criteria	(check appropriate box)	
Male below 13 years	Yes 	No 
Correct fitting ShangRing size is not available	Yes 	No 
Has the following diseases: hypospadias, hydrocele, scrotal hernia, balanitis, epispadias	Yes 	No 
Known bleeding/coagulation abnormality	Yes 	No 
Is cognitively impaired	Yes 	No 
Has a serious chronic illness, which is not well-controlled (subject not feeling well or has significant medical complaints)	Yes 	No 
Has an active genital infection, current urethral discharge, or other STI symptom	Yes 	No 
Has another condition, which in the opinion of the supervising circumcision coordinator (a medical doctor) prevents the subject from undergoing circumcision with the ShangRing device	Yes 	No 

Any "YES" answer disqualifies the subject from participating in the evaluation

Client's CID:

INFORMED CONSENT VERIFICATION

Has the client been informed according to the protocol? Yes No

Has the consent been obtained **before** any evaluation related procedures? Yes No

Has the client signed the photography consent form? (Declining photography does not exclude the client from participating) Yes No

Has the client provided a phone number and agreed to be contacted by evaluation staff Yes No

Has the client signed the consent form? Yes No

Consent Date: _____

Has the client been provided with a photocopy of the signed consent form? Yes No

Does the client agree to participate in the in-person qualitative interview three weeks post-removal? (If yes have client complete in-person interview consent during post-MC counseling) Yes No

Does the client agree to return for a healing assessment 6 weeks post-removal, and subsequent weekly healing visits if not healed at 6 week post-removal visits? Yes No

Date of Birth (day/month/year): _____

Age in Years: _____

Include a copy of the signed consent with this form in client evaluation file

Client's CID:

CLIENT CONTACT INFORMATION

First Name: _____ **Surname:** _____

Contact number(s) **Home:** _____ **Mobile:** _____

Work: _____

Preferred time to receive evaluation calls: _____

Address and description of area of residence: _____

Place of employment: _____

Family member/friend name: _____

Contact number(s): _____

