Potential clients will receive a medical history screening and a genital examination conducted by the VMMC provider to determine that they are in overall good physical health. Additional inclusion criteria include the following:

- Male aged 13 years and older
- Uncircumcised following physical assessment
- Seeking medical circumcision at one of the evaluation sites

- Consents to an HIV test.
- Agrees to be circumcised using the ShangRing device
 - Those aged 13-17 years will also require parental/guardian approval in order to be included in addition to providing assent. Parents must also agree to be present at the facility during the circumcision (though not in the operating room unless requested by the client), for the discharge instructions, and for subsequent follow-up visits.
- Penis fits into one of the 18 ShangRing ring sizes
- Able to understand the evaluation procedures and requirements
- Agrees to abstain from sexual intercourse and masturbation, for six (6) weeks post removal, seven (7) weeks total
- Lives within 30 kilometers of the facility in Shinyanga, Tanzania
- Willing to provide valid contact information (i.e. telephone number, address of residence, place of employment and other locator information) and willing to receive communications and/or follow-up visits, clients may also be asked for names of relatives or friends to be contacted in the event that the client cannot be reached
- Has an activated cell/mobile phone or access to a cell/mobile phone
- Agrees to return for a follow-up visit to assess healing day 49 post-placement (42 days post-removal).
- If not healed at the day 49 post-placement visit, agrees to return for weekly follow up visits until healed.
- Agrees to a 10 day post-placement (3 days post-removal) telephone call to assess and detect symptoms of AEs
- Able to communicate in English and/or Swahili
- Capable and willing to provide written informed consent (18 years and older), or written informed consent from a parent guardian (13-17 years) to participate for both HTS and VMMC services.

Client Exclusion Criteria

Clients who do not meet the inclusion criteria above and who have the following known medical conditions will be excluded from the evaluation:

- Cognitive impairment that prevents the client from providing consent

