- Any health condition (reported or observed) that is a contraindication to surgical VMMC in the national program, or that ShangRing providers deem a contraindication. These may include diabetes, peripheral vascular disease, cancer, bleeding disorders, and/or current moderate or severe infectious illness.
- Known **uncontrolled** diabetes, hypertension or tuberculosis (TB)
 - Note: if a client has **controlled** diabetes they may still be eligible for circumcision, but blood sugar should be checked first. If the check reveals blood sugar to be acutely elevated, defer circumcision until blood sugar is better controlled.
- Acute illness, other than colds or other minor complaints
- Active skin infection
- Anatomical variations and anomalies of genitalia:
 - Hypospadias, epispadias, or other urethral anomaly; except for glanular hypospadias, which is not a contraindication if provider is experienced
 - Hydrocele or other scrotal swelling
 - Scrotal hernia
 - Phimosis or paraphimosis
 - Other genital anomaly or disease including infectious or traumatic ulcers, or scarring involving frenulum, foreskin or glans
 - Dermatitis of the penis or foreskin, filariasis or penile cancer

- Genital warts involving both foreskin and glans (note: genital warts involving only foreskin are not a contraindication if provider is experienced)
- Urethral discharge
- Balanitis or posthitis (clients with balanitis should be referred to a specialist, as circumcision is likely to be necessary but should be done by an experienced provider)
- Current sexually transmitted infection (STI) other than HIV (clients with STIs can return for circumcision once STI is treated)
- Other conditions, which in the opinion of the supervising circumcision coordinator, prevents the subject from undergoing a circumcision with the ShangRing device

Clients who do not meet inclusion criteria will be offered standard surgical circumcision if not contraindicated. The number and reasons for such exclusions will be recorded and included in the final evaluation report.

Medical Referral

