Sites should provide a brief orientation to other health centers in the catchment area. The purpose of this orientation is to provide these health centers with an overview of the pilot, to offer the health centers guidance on how to provide care for any pilot clients that may present to their clinic, and to request the health centers alert the pilot sites in the event that a client from the pilot seeks follow-up care from the center (i.e. in the case of the AE), and provide the health centers with contact information for implementation pilot staff in order to do so.

Sample Size, Data Collection and Analysis Timeline

The total sample size for this implementation pilot is 575 male clients at the selected sites in Shinyanga, Tanzania. Both HIV- and HIV+ men will be included in the sample. The sample size of 575 males is consistent with the framework for circumcision device introduction as proposed by the WHO (see appendix I below). Additionally, this sample size is powered to detect the occurrence of adverse events, which is estimated to be 2%. A minimum of 335 males are necessary for 95% confidence that the population proportion is within $\pm 1.5\%$ with an observed adverse event rate of 2%. An additional 240 males will be recruited for further confidence in the results, and to align with the WHO framework. The evaluation teams will enroll males until the 575 sample size figure is achieved. All 575 males to be considered for the data analysis will be enrolled upon completion of the training phase.

All data collection will begin as soon as the first circumcision of an enrolled client occurs. Data will continue to be collected until the country has performed 575 circumcisions with the ShangRing device, and all post-circumcision follow-up data collected from clients as detailed in this protocol is complete. After the 575 circumcisions and all follow-up information is collected, the analysis of data as described per the primary and secondary endpoints will begin. If after the country has finished 575 circumcisions, and wishes to conduct the analysis necessary to inform national policy for the purposes of implementing the ShangRing device on a wider scale, that country may continue to enroll clients, and the first 1000 circumcisions performed should be monitored through active surveillance, as detailed in the WHO framework, and the country should perform its own data analysis as needed.³¹

Supplies and Logistics

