Written informed consent is required by the MoHCDGEC and the National Institute for Medical Research (NIMR). Eligible clients for this evaluation will read and/or have read to them the written consent form in English or the local language. Men aged 13-17 will also have a parent/guardian present to read/have read to them the written consent form in English or the local language. Eligible clients also will have the opportunity to have any questions answered by an evaluation nurse. Informed consent will cover evaluation procedures, potential risks, benefits, and contact persons for reporting complaints or concerns. Procedures will also be put in place to protect confidentiality of the client, and these procedures will be explained to the client prior to their enrollment. Evaluation nurses will explain the procedure and follow-up visits in detail including the need to take confidential photographs of the healing wound at follow-up visits. Evaluation nurses will tell potential clients that the procedure will provide to them safe male circumcision and help the MoHCDGEC to understand the best way to scale-up male circumcision and make it more accessible as one of the prevention strategies for HIV infection. Evaluation nurses also will notify potential clients that they have the right to withdraw from the evaluation at any time; however, if they choose to withdraw after the ShangRing device has been placed, they will need to wait at least 5 days before the device can be safely removed by trained staff. Males who test positive for HIV during screening will still be offered the opportunity to receive a ShangRing circumcision, and these men will receive additional counseling and referral for HIV care and treatment services as described below.

After the contents of the consent form are clearly understood by clients, they (and their parent/guardian, if applicable) will be asked to sign all or part of their name if they accept ShangRing circumcision and agree to follow-up visits. Clients who are unable to sign their name will be allowed to make a digital impression (i.e., thumbprint).

A copy of the signed consent form will be provided to clients and their parent/guardian if applicable (see Appendices III-VI for different consent forms). Another copy of the consent form will be maintained in the site's evaluation files in a locked file cabinet with access limited to evaluation staff.

Eligibility Screening

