The potential client's eligibility will be assessed through a medical history screening and a genital examination, which cover the inclusion criteria listed above and helps to ensure that the client is in overall good physical health. The screening and examination will be documented on evaluation forms (see Appendix VII).

Potential clients who are not eligible to participate in the evaluation will be offered standard surgical circumcision, if their reason for ineligibility does not likewise disqualify them from receiving a standard circumcision. The number and reasons for ineligibility will be recorded and included in the final evaluation report (See Appendix XII).

HIV Testing Procedures

Serological testing for HIV, which follows national standards established and approved by the Tanzanian MoHCDGEC, is a standard component of male circumcision services globally.

HIV rapid testing will be conducted after receiving written informed consent, and completion of pre-test counseling by certified personnel. Per national guidelines, any person above the age of 18, or any mature minor less than 18 years of age may give informed consent to receive HTC services. A mature minor is defined as any person below 18 years of age who is married, sexually active, or otherwise believed to be at risk for HIV infection. A young person below 18 years of age who does not meet the definition of a mature minor may receive HTC services with the written consent of a parent or legal guardian. Tanzanian national HIV guidelines for HIV counseling, testing and referral services will be followed and pre-test counseling will include an explanation of HIV infection and transmission, the meaning of test results, and risks associated with sexual behaviors. Rapid testing will be conducted using the national algorithm in Tanzania. Clients will be tested using the standard national algorithm and tests. Clients will be informed of the result of their test verbally by a counselor upon its completion.

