All potential clients will receive post-test counseling, with specific messages tailored to their test result. Men with negative results will be counseled on strategies for behavioral risk reduction, maintenance of risk reduction and explanation of risk reduction methods (e.g., condom use) before they provide consent for ShangRing circumcision. Men with positive results will be given referral to HIV care services and further counseling and testing, and can receive ShangRing or surgical circumcision that day if still desired and they are otherwise eligible. The counselor will inform them of any additional health assessments required under MoHCDGEC policy for them to access ShangRing or surgical circumcision. If rapid test results are indeterminate, per national guidelines the provider will immediately repeat the test following testing instructions, or another HTC provider/lab technician will repeat the test. If the test is still indeterminate, the client will be retested in two weeks.

All samples and specimens collected as part of routine HIV serological testing will be disposed of in accordance with Tanzanian MoHCDGEC VMMC program guidelines.

Evaluation Identification Code

This evaluation will use evaluation identification (ID) codes for the various documents related to the evaluation including the CRF, photographs and surveys. The use of evaluation codes will link evaluation documentation with consent forms, which contain client names and signatures. An evaluation ID code will be created for every client. The master list, linking the ID codes with actual clinic records and the client's name, will be maintained by the site coordinator in a locked file cabinet in a locked office separate from all other evaluation files.

The evaluation ID will be an alphanumeric code created by elements related to the evaluation.

- Site location (Initials of site location)
- Date of enrollment
- Client number (consecutive)

In this regard, the first client enrolled at Good Hope Health Center (fictitious example) on September 1 would have the following evaluation ID code: GH0109001.

Male Circumcision Using ShangRing Device

The ShangRing device contains the following items: two concentric plastic rings, the inner of which is lined by a silicone pad, a measuring tape, and bandages. These must be discarded after each use. The ShangRing device

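### The screening form disqualifies HIV-positive men, whom the protocol body says the sample will include

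*Protocol*

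**What the plan says.** The form, Appendix VII, Eligibility Confirmation:

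- One row of the inclusion table is "HIV sero-negative", with Yes and No boxes.
- Under that table, any NO "answer disqualifies the subject from participating in the evaluation". No footnote or exception covers the HIV row.

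The protocol body:

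- Client Inclusion Criteria: the only item on HIV is "Consents to an HIV test".
- Client Exclusion Criteria: the item on sexually transmitted infection reads "Current sexually transmitted infection (STI) other than HIV", so HIV is carved out.
- Sample Size, Data Collection and Analysis Timeline: "Both HIV- and HIV+ men will be included in the sample".
- Written Informed Consent: "Males who test positive for HIV during screening will still be offered the opportunity to receive a ShangRing circumcision".
- HIV Testing Procedures: men with a positive result "can receive ShangRing or surgical circumcision that day if still desired and they are otherwise eligible".
- Medical Referral: HIV-positive men who are not on antiretroviral therapy are referred for it. This is not stated as a reason to exclude them.

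The Eligibility Screening section names Appendix VII as the place where screening and examination are documented.

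**The concern.** A protocol defines the population, but site staff enrol from the form. Here the form carries an eligibility condition that the protocol does not contain and that its text contradicts in several places.

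If the form is followed, three things happen:

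- HIV-positive men are refused a device that the body says they will be offered.
- The safety, healing and acceptability results describe HIV-negative men only, while the protocol describes a cohort of both.
- The final report, which is to give the numbers and reasons for ineligibility, shows HIV as a reason that the protocol does not recognise.

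The two sites, or staff within a site, could also resolve the conflict differently. Enrolment would then depend on who did the screening. Men turned away cannot easily be recovered later.

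**Working it through.** The finding is a contradiction in the text, so the main check is to follow one man through both documents.

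**An otherwise eligible, consenting man tests HIV-positive at screening.**

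| Step | Protocol body | Appendix VII |
|---|---|---|
| HIV inclusion item | Consent to the test: met | Sero-negative: the truthful answer is No |
| HIV as an exclusion | Carved out of the infection exclusion | Not listed as an exclusion; handled by the inclusion row |
| Result | May receive the device, the same day if he wishes | Disqualified |

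The form offers no way round this. Its completion instructions tell staff to fill every box and to add no wording unless required. They reserve NA for data not relevant to the subject, and HIV status is relevant because every client must consent to testing. The body's own criterion, consent to a test, does not appear in the form's inclusion table.

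**Plan's own sample-size figure.** With an adverse event rate of 2% and a half-width of 1.5 percentage points:

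n = 1.96² × 0.02 × 0.98 / 0.015² = 334.6, rounded up to 335. This reproduces the stated minimum.

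At n = 575 the half-width is 1.96 × √(0.02 × 0.98 / 575) = 1.14 percentage points. Neither figure depends on HIV status, and enrolment continues to 575 under either text.

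**Number of men affected.** Expected HIV-positive men = N × prevalence. The protocol gives 3.5% for men aged 15–64 nationally and 7.4% for Shinyanga in 2011 (not split by sex). It gives no figure for circumcision clients, so these are illustrations. The 1% row is an assumption, for a younger client mix.

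| Prevalence | N = 575 | Implementation phase only, N = 455 to 495 | Under the form |
|---|---|---|---|
| 1% (assumed) | 5.8 | 4.6 to 5.0 | 0 |
| 3.5% | 20.1 | 15.9 to 17.3 | 0 |
| 7.4% | 42.6 | 33.7 to 36.6 | 0 |

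**Effect on the overall adverse event rate.** Table 1 of the protocol gives total adverse event rates of 1.2% (HIV-positive) and 1.7% (HIV-negative). Its footnote gives 3.0% and 2.6% with additional men included. Removing a 7.4% share shifts the overall rate by 0.074 × (1.7 − 1.2) = 0.037 percentage points on the first pair, and by 0.074 × (3.0 − 2.6) = 0.030 on the second. Both are negligible beside a half-width of 1.14.

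**The case against.** The strongest reply is that this is one stray row and the design itself is settled. Every statement on HIV status in the body points the same way. The second eligibility check, in Appendix IX Part 1, has no HIV-status item. The acceptance log in Appendix XVI lists unwillingness to be tested as a reason for declining, which fits a rule of consent to testing. Staff are to be trained on the protocol, so a complete shut-out is the worst case and may not occur.

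The effect on the stated analyses is also small. The Analysis Overview gives an overall adverse event rate with a confidence interval, broken down by site, cadre and training phase but not by HIV status, and that overall rate barely moves. Even with the form corrected, data on HIV-positive men would be thin. With no events in 20 men the one-sided 95% upper bound is 1 − 0.05^(1/20) = 13.9%; in 43 men it is 1 − 0.05^(1/43) = 6.7%.

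The protocol sets no quota either. It requires only that men not be refused because of their HIV status. The prevalence figures may overstate the count: clients are enrolled from age 13, and the regional figure covers both sexes while national prevalence is higher in women (6.5% against 3.5%).

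All of this stands as a limit on size. None of it removes the contradiction. Clear intent in the body does not help when the form used to decide eligibility says otherwise and has no exception. Thin data on a group the protocol names is still different from none.

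**Conclusion.** The concern holds. Appendix VII contains a disqualifying condition that the protocol body contradicts in its inclusion list, exclusion list, sample-size, consent and HIV-testing sections. If the form is followed, the number of HIV-positive men enrolled is zero whatever their prevalence among clients. At the prevalences the protocol cites, the group lost is about 20 to 43 of 575; at an assumed 1% it is about 6. These counts assume that clients resemble the populations surveyed.

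The damage is to who is enrolled and to what the results can be said to cover. The sample size, the precision and the overall adverse event rate are essentially unaffected. Whether sites would in practice follow the form or the body cannot be told from the protocol. The point must still be fixed, because the form as written gives the wrong enrolment decision for every otherwise eligible HIV-positive man.

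**What to change.** In the Appendix VII inclusion table, delete the row on HIV status and put the body's own criterion, consent to an HIV test, in its place. The rule that any NO disqualifies can then stay as it is.

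No new data field is needed. Items 20 and 21 of the client form in Appendix VIII already record whether the man was tested, the date and the result.

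If any clients have already been screened on the present form, review the screening records for men marked ineligible on this row and report their number.

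The cost is one row on one form. Sample size, visits, procedures and analysis do not change.

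### The screening form's disqualifying checklist does not match the protocol's inclusion criteria: it adds survey agreement, narrows parental attendance, and leaves the day 10 and day 49 agreements outside its rule

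*Protocol*

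**What the plan says.** The protocol's Client Inclusion Criteria make four follow-up commitments conditions of entry:

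- the telephone call: "Agrees to a 10 day post-placement (3 days post-removal) telephone call to assess and detect symptoms of AEs"
- the healing visit: "Agrees to return for a follow-up visit to assess healing day 49 post-placement (42 days post-removal"
- further visits: "If not healed at the day 49 post-placement visit, agrees to return for weekly follow up visits until healed"
- for ages 13 to 17, parental attendance: "Parents must also agree to be present at the facility during the circumcision", and also "for the discharge instructions, and for subsequent follow-up visits"

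That list says nothing about agreeing to surveys.

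The Eligibility Screening section states that screening covers the listed criteria and is documented on Appendix VII. In the eligibility table of that form a single No to any inclusion item excludes the man. The table includes "Agrees to complete brief evaluation surveys to assess satisfaction: post-placement and post-removal" and, for minors, "If 13-17 years old, parent/guardian agrees to be present during circumcision". It has no item for the day 10 call, the day 49 visit or the weekly visits.

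The next block of the same form, Informed Consent Verification, asks "Does the client agree to return for a healing assessment 6 weeks post-removal" and, in the same question, about the weekly visits. It also asks whether the client gave a phone number and agreed to be contacted. That block prints no disqualifying rule.

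**The concern.** Site staff will work from the form, so where the form and the protocol differ, the form is likely to decide who enters. Two kinds of error are possible.

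The form can be stricter than the protocol. A man who meets every protocol criterion but does not want to fill in a satisfaction questionnaire fails the table. The Eligibility Screening and Analysis Overview sections have the ineligible counted, with reasons, and reported as a proportion. A survey refusal could then sit in the same figure as men for whom the device is unsuitable.

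The form can also be looser than the protocol. The Primary Endpoint section places adverse event assessment at, among other times, three days after removal and day 49, and day 49 also supplies the healing endpoint. Under Follow-Up Visits, a client who does not attend on day 49 and has not withdrawn is classed as lost to follow-up. Missed visits other than day 7 are normally pursued by phone or text only, and the Analysis Overview rules out imputation. Agreement to these contacts is therefore worth securing at entry, and the protocol's list does so. The form's disqualifying table does not.

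**Working it through.** No figure in the protocol is attached to this point, and the sample-size calculation does not depend on it. The check is an item-by-item comparison of the Client Inclusion Criteria with Appendix VII.

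1. **Satisfaction surveys.** Protocol list: absent. Form: in the table, so a No excludes. Elsewhere, the Data Collection section lists the surveys as planned procedures at day 0 and day 7, and the survey introductions (Appendices X and XI) let the client refuse any question. Result: one criterion added.
2. **Parental attendance, ages 13 to 17.** Protocol list: circumcision, discharge instructions and subsequent follow-up visits. Form: circumcision only, and no other item in the screening form covers the rest. Result: one criterion narrowed.
3. **Day 10 call.** Protocol list: required. Table: absent, although phone access and valid contact information are in the table and disqualifying. Consent verification block: general agreement to be contacted, with no mention of an adverse event call. Result: covered in substance, not named.
4. **Day 49 visit.** Protocol list: required. Table: absent. Consent verification block: asked explicitly, with six weeks after removal being day 7 + 42 = day 49. No consequence is printed for a No. Result: recorded but not tied to eligibility.
5. **Weekly visits if not healed.** Same position as item 4, in the same question.

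Of the four follow-up conditions in the protocol (items 2 to 5), three are missing from the table and one is narrowed. Of the three missing, two are asked in the next block of the form and one is covered only in general terms. One condition (item 1) appears in the table and not in the protocol.

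A later form would not catch the difference. The eligibility confirmation in the device form (Appendix IX) covers good health, counselling, consent and, for minors, parental consent with assent. It does not return to follow-up commitments or parental attendance.

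**The case against.** The strongest reply is that the table is not the whole entry gate. Under Written Informed Consent, the client, and the parent where applicable, signs if he accepts the procedure and agrees to follow-up visits. The Recruitment section admits only those who have consented and meet the eligibility criteria. A reader might infer from the form that a site is free to enrol a man who refuses the day 49 visit. The document does not support that, because such a man should not have signed. The consent verification block also prints no rule for an unsigned consent form, and an unsigned form plainly bars entry, so a missing rule does not by itself mean that a No is acceptable. Photography carries an express exemption in that block, which suggests that optional items were flagged. The qualitative interview is optional and is not flagged, so that inference is not conclusive. This reply stands in part: it limits the practical effect of items 3 to 5, but a separately recorded No still has no stated consequence.

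On minors, the Acceptability Component and Reimbursements sections expect a parent to accompany them to follow-up visits. The consent and assent forms (Appendices II to VI) were not in the copy reviewed and may record that agreement. It is therefore not established that minors would be enrolled without it. The narrower wording of the screening form remains.

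On surveys, a reader might infer that excluding decliners biases the acceptability results. That does not follow for the survey results, since a man who declines gives no survey data whether he is enrolled or not. Agreeing to take a survey is also compatible with being free to skip a question. What remains is that the protocol does not make this agreement a condition of entry and the form does.

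**Conclusion.** The contradiction is real and modest. Survey agreement is an added disqualifying item, parental attendance is narrowed, the day 10 call is not named, and a No to the day 49 and weekly visits is not linked to ineligibility although the protocol makes agreement a condition.

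The effect on the adverse event rate and the healed percentage is probably small and cannot be quantified from the document. It is tempting to assume a refusal rate and bound the healed percentage, but the protocol gives no such rate. The bounds would describe loss to follow-up from any cause and could not be attributed to the form. The effect on the reported ineligible proportion is likewise of unknown size, and survey refusals could be separated out if their reason is recorded as planned.

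The conclusion rests on two assumptions: that sites use the Appendix VII table as their working eligibility check, and that the consent procedure is applied as written.

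**What to change.** Reconcile Appendix VII with the Client Inclusion Criteria before enrolment:

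- Take survey agreement out of the disqualifying table and record it as a non-disqualifying item, as is done for photography. If the sponsor means it to be mandatory, add it to the Client Inclusion Criteria instead.
- Extend the parental item for ages 13 to 17 to the discharge instructions and subsequent follow-up visits.
- Name the day 10 adverse event call in the table.
- Move the day 49 and weekly visit agreement into the table, or state beside the existing question that a No makes the client ineligible.

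The cost is a revision of one page of one form. The downside is that a few men unwilling to return would not be enrolled, which is what the protocol's own criteria already intend. The HIV sero-negative item in the same table conflicts with the protocol's plan to include HIV-positive men. It is a separate and more serious matter, and the same revision could address it.
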